### 7.2.2 Recording Procedures for All Adverse Events

All observed or volunteered adverse events, regardless of treatment group or suspected causal relationship to study drug, will be recorded as an Adverse Event in the case report forms at each study visit. Adverse events should be collected from the time the patient provides informed consent to participate in the study until 30 days after the last dose of study medication. Events involving adverse drug reactions, illnesses with onset during the study, or exacerbation of pre-existing illnesses should be recorded. Objective test findings (e.g., abnormal laboratory test results) that result in a change in study drug dosage should also be recorded.

All AEs will be recorded on the CRFs provided. A description of the event, including its date of onset and resolution, whether it constitutes a SAE or not, the date it became serious, seriousness criteria (e.g. fatal, life-threatening, hospitalization, disability, congenital anomalies), any action taken (e.g., changes to study treatment, other treatment given and follow-up tests) and outcome should be provided along with the Investigator’s assessment of causality to the study drug, study medication and study procedure.

It will be left to the treating physician’s clinical judgment whether or not an adverse event is of sufficient severity to require that the subject should be removed from treatment. A subject may also voluntarily withdraw from treatment due to what she/he perceives as an intolerable adverse event. If either of these occurs, the subject will be given appropriate care under medical supervision until the symptoms cease or until the condition becomes stable.

The severity of toxicities will be graded in accordance with the Common Terminology Criteria for Adverse Events Version 3.0 (<http://ctep.cancer.gov/forms/CTCAEv3.pdf>). A link to CTCAE v3 is also provided in the study database in the adverse event CRFs.

## 7.3 Adverse Event Reporting

### 7.3.1 Reporting Procedures for Serious Adverse Events

Reporting of SAEs will be managed by SARC. Full details for the procedures to be adopted will be documented in the Safety Reporting Plan approved by the responsible parties.

#### **Initial notification of serious adverse events**

The treating physician or other site personnel must report all serious adverse events within 24 hours to the study coordinator at SARC.

All SAEs must be reported, whether or not considered causally related to the investigational product or to the study procedure/s. All SAEs will be recorded in the CRF.

All serious AEs (SAEs), whether considered related or unrelated to investigational product, must be reported immediately (**within 24 hours of awareness**) by the investigational site to SARC, the Study Principal Investigator, and AstraZeneca Patient Safety by confirmed facsimile transmission. If only limited information is initially available, follow-up reports are required. The original SAE form must be kept on file at the study site.

SAEs should be reported on the MedWatch Form 3500A, which can be accessed at: <http://www.accessdata.fda.gov/scripts/MedWatch/>. The MedWatch form must be completed using the following guidelines:

- The date the site notified SARC and AstraZeneca of the SAE must be specified in the “Describe event” narrative section.
- Initial and follow-up MedWatch reports should be numbered either in the narrative section or in section G.7 of the MedWatch form.
- If more than one SAE is listed on the MedWatch form, each event should be numbered.
- Institutional Principal Investigator must designate causality to study drug for each SAE and must be specified in both the “Describe event” narrative section of the MedWatch form and the SARC012 SAE Fax Coversheet.
- There will be 2 causality designations: Yes = Related to study drug, No = Unrelated to study drug
  - If there is any possibility that the SAE is related to study drug, then designate Yes for causality.
  - If there is clearly no possibility that the SAE is related to study drug, then designate No for causality.
- If the SAE is considered to be related to a study procedure, this should also be indicated in the narrative section

For all SAEs, completed MedWatch forms along with a completed SAE Fax Coversheet (Appendix C) should be faxed to SARC, the Study Principal Investigator, and AstraZeneca Patient Safety **within 24 hours** of awareness of the event. The SAE Fax

### **Reporting of serious adverse events**

SARC will determine the reportability of the event and will send expeditable reports to the FDA within the required timelines. The Research Project Manager at SARC will be responsible for sending these expeditable reports to the Study Leader at AstraZeneca at the same time that they are reported to the FDA.

SARC will also provide full written reports of all SAEs to:

- STUDY PRINCIPAL INVESTIGATOR. [name] ([contact]).
- INSTITUTIONAL PRINCIPAL INVESTIGATOR.
- SARC will email expedited reports to all local sites involved in the study within 2 business days of receipt, and local sites will process per institutional policy.

SARC will send Safety Reports received from AstraZeneca to all sites involved in the study within the timelines required by the FDA, and local sites will process per institutional policy.

### 7.3.2 Adverse Event Reporting Procedures to the Investigator's IRB

The Principal Investigator of each participating site is responsible for reporting to their local IRB all events that occur in participants enrolled at the site according to the policies and procedures of the institutional IRB.

## 7.4 Treatment Regimen Unblinding

See Operations Manual for process to request patient treatment regimen unblinding.

### 7.4.1 Criteria for Unblinding for Serious Adverse Events

The following events require unblinding of treatment assignments in this study:

1. The occurrence of a serious adverse event that is both unexpected and considered by the reporting investigator to be associated with the use of study drug, and the knowledge of the treatment assignment is deemed essential for the patient's care.
2. An unexpected serious adverse event occurs and the intervention must be made known for purposes of reporting to the FDA (SARC responsibility as Study Sponsor).

Unblinding of treatment assignments for patients on this study will be performed by authorized SARC personnel, upon approval from the SARC Medical Officer or designee.

Requests for unblinding by the site should be only for urgent patient safety issues.

**Note: To ensure patient safety, if need be, all discussions can be done verbally with written documentation to follow once patient safety secured.**

Any patient whose treatment assignment is unblinded because of a serious adverse event(s) will be removed from study treatment and followed only for survival. The site should continue to follow the patient status regarding the serious adverse event(s) for which the patient's treatment was unblinded until resolved or improved to baseline and the patient can receive additional off-study treatment as necessary.

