## 2.3 Patient Enrollment

[figure not shown]
A signed informed consent document will be obtained prior to entry onto the study. Following consent, patient information is entered in the eCRF database. All patients must have histological verification of recurrent osteosarcoma in the lung prior to randomization. A copy of the pathology report documenting histologic confirmation should be sent to the SARC RPM prior to randomization.

Enrollment will be centrally managed by the trial coordinating center, SARC. Patient data will be entered electronically by the participating institutions through the study website:

<https://velos.med.umich.edu/eres/jsp/ereslogin.jsp>

Each patient will be assigned a patient identification number automatically following enrollment. Patients can be enrolled at any time of the day, any day of the week, via the website.

Once the patient has undergone complete surgical resection and the institutional PI determines that all of the criteria for inclusion have been met per protocol Section 2.1, the eligibility CRF will be completed in the database. The patient can then be randomized.

Patients will be registered and then stratified based on the number of recurrences (FIRST versus SECOND versus THIRD or MORE) and the number of recurrent nodules (ONE or TWO versus THREE or MORE).

SARC will possess separate randomization sheets for each stratum. Patient treatment assignment will be kept confidential and will not be shared with the treating physician(s) or any other site team staff involved in the care of the patient, except in the event of a medical emergency where unblinding is necessary to ensure patient safety (See Operation Manual for details), or at the time of recurrence if the recurrence is in the lung. (See Section 7.4.2).

Any questions regarding eligibility or the randomization process can be addressed to the SARC Operations Office:

SARC Research Project Manager  
[name]  
[name]  
[name]  
[name]  
[contact]  
[contact]  
Email: [contact]

SARC, the study Principal Investigator and the Principal Investigators at each participating institution will have access to this website to review data regarding this clinical trial.

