##### Non-Hematological

- Any CTCAEv3 grade  $\geq 3$ , non-hematological toxicity (with the exception of alopecia, nausea and vomiting)
- CTCAEv3 grade  $\geq 3$ , hypophosphatemia (see section 3.3.3 for modified dose reduction schema)
- CTCAEv3 grade  $\geq 3$  nausea or CTCAEv3 grade  $\geq 3$  vomiting, lasting  $>24$  hours despite IV fluids, anti-emetic therapy and adequate supportive care
- Chronic CTCAEv3 grade 2 nausea or vomiting

In the event of any toxicity, of any grade, that the treating physician suspects is due to disease progression, re-evaluation of tumor status is indicated, irrespective of scheduled clinic visits.

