### 3.3.2 Dose Reduction of Oral Therapy

If a patient experiences any of the toxicities defined in section 3.3.1, or another unacceptable toxicity occurs, and the investigator considers that the event is related to the study drug, oral therapy will be stopped for a maximum of 21 days, and supportive therapy will be administered as required. If the toxicity resolves or reverts to a CTCAEv3 grade 0 or grade 1 or to the baseline (pre-study) grade within 21 days of onset, oral therapy will be restarted at a lower dose as follows:

If a patient is currently taking 175 mg, the lower dose will be 125 mg.

If a patient is currently taking 125 mg, the lower dose will be 100 mg.

A maximum of two dose decreases, for any individual patient, can be made during the study period, down to the lowest dose of 100 mg of saracatinib or placebo.

If a patient experiences any of the toxicities defined in Section 3.3.1, or another unacceptable toxicity occurs, while taking 100 mg, then the patient must be withdrawn from the study. For all patients who experience any of the toxicities defined in Section 3.3.1, or another unacceptable toxicity occurs during the study, if the toxicity does not resolve to CTCAEv3 grade 0 or grade 1 or to the baseline (pre-study) grade within 21 days of onset, then the patient must be withdrawn from the study. Patients will continue to be monitored until the toxicity has resolved.

Patients will continue to be monitored for overall survival for the duration of the study. If patients have toxicity that requires their removal from the study prior to ascertainment of disease progression, then these patients will be considered treatment failures in the time to treatment failure analysis and the duration of total treatment will be included in the time to treatment failure. However, for the progression free survival analysis, withdrawals due to toxicity will be censored, as the subject has not progressed.

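### Section 7.4.1 as worded removes patients whose code SARC breaks only for FDA reporting, conflicts with the restart rule in 3.3.2 for some events, and ends scheduled progression assessment for the primary endpoint

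*Combined protocol and SAP*

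**What the plan says.** Section 7.4.1 gives two reasons for breaking the code after a serious adverse event (SAE). The first is an unexpected SAE that the investigator links to study drug and for which the assignment is essential to the patient's care. The second is: "An unexpected serious adverse event occurs and the intervention must be made known for purposes of reporting to the FDA". The protocol marks this second one as SARC's responsibility as sponsor. Authorized SARC personnel perform the unblinding with approval from the SARC Medical Officer or a designee, and "Requests for unblinding by the site should be only for urgent patient safety issues".

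The consequence is then stated once, for both triggers: "Any patient whose treatment assignment is unblinded because of a serious adverse event(s) will be removed from study treatment and followed only for survival". The next sentence asks the site to keep following the SAE itself until it resolves or returns to baseline.

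Section 3.3.2 covers the toxicities listed in 3.3.1 and any other unacceptable toxicity. If "the investigator considers that the event is related to the study drug, oral therapy will be stopped for a maximum of 21 days". If the toxicity resolves to grade 0-1 or baseline "within 21 days of onset, oral therapy will be restarted at a lower dose as follows". Section 3.3.3 allows 35 days for hypophosphatemia. At the lowest dose level, 3.3.2 requires withdrawal instead. Section 3.3.2 also says that withdrawals for toxicity are censored in the PFS analysis.

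Section 2.3 keeps the assignment from the treating physician and site staff "except in the event of a medical emergency where unblinding is necessary to ensure patient safety", or at a lung recurrence. Section 5.3.1 says much the same. The removal criteria in section 3.7.2 do not list unblinding. Patients taken off study get annual survival contact through their physician, for at most 3 years.

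**The concern.** Under the second trigger the code is needed by the sponsor, for a regulatory report. Nothing in that trigger says that the site needs to know the arm or that the patient's condition calls for stopping. Yet the removal sentence applies to any patient unblinded because of an SAE, so a reporting act can end study treatment and scheduled progression assessment.

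Two things are at stake. The first is conduct: the same event can be governed by two mandatory rules with opposite outcomes. The second is the primary endpoint: patients leave progression assessment for a reason connected with adverse events. If such events are more frequent on saracatinib, and if the patients who have them differ in prognosis, the resulting censoring is informative and the PFS comparison can be biased in either direction.

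**Working it through.** **Step 1: the two treatment rules side by side.** Take a toxicity that is unexpected, serious, judged drug-related, within 3.3.1 (or otherwise unacceptable), above the lowest dose level, and resolved within the hold period. Suppose SARC breaks the code for an FDA report.

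| Source | Outcome for study treatment | Refers to the other rule? |
|---|---|---|
| 3.3.2 (or 3.3.3) | Restarted at a lower dose | No |
| 7.4.1 | Removed | No |
| 3.7.2 removal criteria | Unblinding not listed | No |

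Both rules are worded as mandatory and no precedence is stated. The overlap is plausible from the protocol's own lists. Section 3.3.1 includes grade 3 or higher hypophosphatemia, and thrombocytopenia with non-traumatic bleeding. Section 8.1.5 does not list hypophosphatemia as expected and lists only mild bleeding. Hospitalization makes an event serious under 7.2.1. Expectedness also depends on the Investigator's Brochure, which is not available here.

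**Step 2: the route to the primary endpoint.** Section 7.4.1 limits follow-up to survival, apart from the SAE. Section 3.7.2 makes off-study contact annual and for survival. The nearest analysis rule, in 3.3.2, censors toxicity withdrawals for PFS. No scheduled scan would therefore capture a later progression.

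**Step 3: reproduce the plan's power.** Inputs from section 5.3: 2-year PFS 33% and 53%, 44 patients per arm, 48 months of accrual, 12 months of further follow-up, one-sided alpha 0.10. Uniform accrual and no other losses are assumed.

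- Monthly hazards: -ln(0.33)/24 = 0.04619 and -ln(0.53)/24 = 0.02645; ratio 1.746 (the plan gives 1.75).
- Event probability: P = 1 - [exp(-12λ) - exp(-60λ)]/(48λ). Control: 1 - (0.5745 - 0.0626)/2.217 = 0.769. Saracatinib: 1 - (0.7280 - 0.2045)/1.270 = 0.588.
- Expected events: 44 × 0.769 + 44 × 0.588 = 33.8 + 25.9 = 59.7.
- Schoenfeld power: Φ(√59.7/2 × ln 1.746 - 1.2816) = Φ(0.872) = 80.8%. Freedman's formula gives 79.3%. The stated 80% is reproduced.
- Events required for 80% power: 59 (Schoenfeld) or 62 (Freedman). Section 5.3 states no dropout allowance.

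**Step 4: effect of removal, under an assumed rate.** The documents give no rate of SAE unblinding. Assume that a share of patients is marked for unblinding at a time uniform over the first 12 months, and is censored then if still progression-free and under follow-up. Censoring is taken as unrelated to prognosis. Simulated with 2 million patients per arm and scenario, scaled to 44 per arm:

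| Assumed share | Patients removed while at risk | PFS events | Events lost | Power |
|---|---|---|---|---|
| None | 0 | 59.7 | 0 | 80.8% |
| 5%, saracatinib only | 1.9 | 58.7 | 1.0 | 80.4% |
| 10%, saracatinib only | 3.8 | 57.7 | 2.0 | 79.9% |
| 5%, both arms | 3.6 | 57.5 | 2.2 | 79.7% |
| 10%, both arms | 7.1 | 55.4 | 4.3 | 78.6% |
| 20%, both arms | 14.3 | 51.1 | 8.6 | 76.1% |

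The table treats every such patient as one who would otherwise have stayed under assessment, so it overstates the loss from 7.4.1 alone. It does not measure bias.

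**The case against.** The strongest defence has four parts.

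- **Scope.** The removal sentence speaks of unblinding because of an SAE and is followed by a reference to off-study treatment, which fits care-driven unblinding. It may have been meant only for the first trigger. That is possible, but the words do not limit it so.
- **Specific over general.** Section 7.4.1 can be read as the specific rule that qualifies 3.3.2. The protocol does not say so. The defence is right that the conflict is narrow: it disappears if the event is judged unrelated, does not resolve in time, or occurs at the lowest dose level.
- **Existing safeguards.** Sections 2.3, 5.3.1 and 7.4.1 already limit who learns the arm. A reader might infer that reporting-only unblinding discloses the arm to the site. The documents do not support that: FDA reporting is not among the listed exceptions, and site requests are confined to urgent safety. The Safety Reporting Plan and Operations Manual may add more but are not available here. This weakens any claim of unblinding at the site; it does not touch the removal sentence.
- **Not unique.** Other toxicity withdrawals are also censored and followed for survival only, and some patients with an SAE would leave under 3.3.2 or 3.7.2 anyway. This stands, but removal that follows from a reporting act is avoidable.

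Three stronger readings should be resisted. First, a reader might say that everything except survival is lost. In fact the SAE is followed, adverse events are collected to 30 days after the last dose (7.2.2), and 3.8 asks for an off-study radiologic evaluation where possible. Second, section 7.3.1 tells sites "If there is any possibility that the SAE is related to study drug, then designate Yes for causality", and one might infer that this makes the reporting trigger very wide. That trigger contains no investigator-causality element, and SARC decides reportability. Third, multiplying an assumed rate by all expected events (10% of 59.7 = 6.0) overstates the loss, because it counts progressions that occur before removal; the table gives 4.3.

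**Conclusion.** The point holds in a limited form. As worded, 7.4.1 applies removal to sponsor-only unblinding. For a defined subset of events it contradicts 3.3.2, with no order of precedence, and it ends scheduled progression assessment for the primary endpoint. The extent is unknown because no rate is given. At an assumed 5-10%, about 1 to 4 of 59.7 events are lost and power falls from 80.8% to between 80.4% and 78.6%, which is small. The larger concerns are inconsistent handling of like events and possible informative censoring. The latter depends on two things the documents do not establish: that such events are more common on saracatinib, and that they relate to prognosis. Which treatment rule should prevail is not a matter for this review.

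**What to change.** 1. Reconcile 7.4.1 with 3.3.2, 3.3.3 and the removal criteria in 3.7.2. State whether unblinding by SARC solely for FDA reporting invokes the removal sentence. The sponsor decides which treatment rule governs.
2. State in 7.4.1 that a code released under the second trigger goes only to the authorized SARC personnel filing the report, with site, patient and outcome reviewers kept blinded, in line with 2.3 and 5.3.1.
3. Replace the survival-only follow-up wording so that progression scans on the section 3.4 schedule continue after SAE unblinding, whether or not treatment stops, and use those data in the PFS analysis.

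The cost is a short amendment, some additional follow-up data collection, and restricted code access within SARC. SARC already performs the unblinding and the scans are already scheduled.

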### 7.4.2 Unblinding for Disease Recurrence in the Lung

Patients who recur in the lung while on-study and who are thought to be amenable to complete surgical resection will be unblinded. Those patients who were receiving placebo may then have the option of undergoing surgical resection. If fully resected,

the patient will be given the option to begin oral therapy with Saracatinib. Patients who recur in sites other than the lung while on-study will be taken off study and will not be offered the opportunity to be unblinded.

Requests for unblinding by the site should be made at the time of recurrence, only if the recurrence is in the lung, and only if the recurrence is thought to be amenable to complete surgical resection. Authorized SARC personnel will perform unblinding of the treatment assignment. Those patients who were receiving Saracatinib will be taken off-study for disease progression (see Section 3.7). Those patients who were receiving placebo will be offered the option of undergoing surgical resection. If complete resection is achieved, the patient will be given the opportunity to receive Saracatinib (see Section 3.2.6).

[figure not shown]
## 8 Pharmaceutical Information

### 8.1 Saracatinib (AZD0530)

#### 8.1.1 Chemical Information

Chemical Name : *N*-(5-Chloro-1,3-benzodioxol-4-yl)-7-[2-(4-methylpiperazin-1-yl)ethoxy]-5-(tetrahydro-2*H*-pyran-4-yloxy)quinazolin-4-amine

Chemical Structure :

Molecular Formula : C27H32ClN5O5

Molecular Weight : 542.04 as free base

Half-life 40 hours in humans

#### 8.1.2 Supplier and Trial Sponsor

AstraZeneca will supply saracatinib and placebo for this trial. SARC (Sarcoma Alliance for Research through Collaboration) will sponsor this trial, which will be conducted under an IND held by SARC (IND #103,268).

#### 8.1.3 Preparation and Storage

Saracatinib tablets will be prepared by AstraZeneca and supplied by a third party vendor to the hospital pharmacy for subsequent distribution to the patient. The tablets are round, pink, film-coated and come in 50 mg and 125 mg doses. Tablets will be packed in child-resistant, tamper-evident, high-density, polyethylene (HDPE) bottles with child-resistant closures. Packaging includes bottles, caps and labels.

Bottle labels will be available for the two different strengths of saracatinib. Saracatinib is presented in plain, round, biconvex, pink, film-coated tablets that contain 50 mg or 125 mg of saracatinib in free base form. The 50 mg tablets have a diameter of 7 mm and the 125 mg tablets have a diameter of 9.5 mm.

Both 50 mg and 125 mg tablets contain saracatinib, mannitol, dibasic calcium phosphate anhydrous, croscopvidone, hypromellose and magnesium stearate. The film-coat contains hypromellose, macrogol 400, red iron oxide, black iron oxide and titanium dioxide.

The tablets should be stored at room temperature in the pack provided. The expiration date will be listed on the product label. For further information, investigators should refer to the investigational product label.

